Temporal differences in TUV_{global} from baseline to 5 ± 1 weeks of therapy ($\Delta TUV_{global[5w]}$) will be compared with longitudinal clinical outcomes at 12 ± 1 and 24 ± 1 weeks of therapy defined by changes in CDAI ($\Delta CDAI_{12/24w}$), changes in DAS28 ($\Delta DAS28_{[12/24w]}$), and assessment of ACR Response Criteria ($ACR_{12/24w}$) to evaluate the efficacy of TUV_{global} for the accelerated prediction of clinical response to antirheumatic drugs.

Tc99 tilmanocept images with low levels of localization in the joints- and thus presumptively low numbers of synovial lining macrophages are thought to be less likely to respond to anti-TNF α therapies, and these cases will be classified as predicted non-responders using their baseline scan alone. The determination of low level of localization is done quantitatively by

applying a threshold TUV_{global} of 5 as the cutoff value. Patients whose baseline scans are determined to have TUV_{global} below this are predicted to be non-responders. This value was determined in the completed Phase 2B trial NAV3-31. Patients whose TUV_{global} scores are 5 or above then have their baseline scans compared to their Week 5 scans to determine if they will be classified as predicted responders or non-responders. A quantitative analysis of their change in TUV_{global} score from baseline to Week 5 is performed to see if their levels of localization have changed significantly. All subjects in this trial will undergo baseline and Week 5 scans, including those whose baseline scans demonstrate TUV_{global} below 5, as an objective is to assess if any longitudinal changes in TUV_{global} from baseline to Week 5 can be predictive of clinical response or non-response. The process of dichotomizing subjects based on their baseline TUV_{global} scores is referred to as bucketing. Statistical analyses will be performed on bucketed data. In the bucketed analyses, subjects with baseline TUV_{global} below 5 are classified as predicted non-responders while those with baseline TUV_{global} above 5 are classified as either predicted responders or non-responders based on the change in TUV_{global} between baseline and Week 5.

The Schedule of Events (Appendix 1) contains a list of all study procedures and time points. Study activities are described in detail in Section 7.

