2.2 Analysis Populations

The following analysis populations will be defined.

Safety population – The safety population includes all patients that have been enrolled in the study and injected with at least one dose of Tc 99m tilmanocept.

Intent-to-diagnose (ITD) population – Patients in the safety population meeting the following criteria are members of the ITD population:

- were injected with Tc 99m tilmanocept at Visit 2 (Day 0)
- received planar imaging of the hands at Visit 2 (Day 0)

This population will include all patients for whom a prediction might be made, although some patients may be excluded from analysis under this definition if a prediction cannot be made due to missing imaging or clinical data.

Per-protocol (PP) population – The PP population will include all ITD patients without major protocol violations. All protocol deviations will be classified as major or minor prior to database lock.

All efficacy analyses will be carried out on the ITD and PP populations with the ITD population being the primary analysis set. All analyses of safety data and baseline patient characteristics will be carried out on the safety population. A data listing displaying the patients excluded from each population will be created, as shown in Appendix B.

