2.5 Calculation of TUV

TUV_{joint} is defined to be the mean pixel intensity of the region of interest (ROI) defined by the reader divided by the mean pixel intensity of the hand reference region. Each of the three blinded readers will have determined the TUV distribution for both anterior and posterior views of the wrists and hands (wrists, MCPs, and PIPs) for the healthy patient normative data set. For all of the following calculations, the reader-specific TUV_{joint} limits will be used. The upper

limit of normal is defined to be the upper limit of the 95% prediction interval of the joint-and-view-specific TUV in the normative data set.

For each RA patient do the following.

Step 1: Calculate TUV_{joint} for each of the 22 DAS28 joints for which data are collected.

Step 2: Identify all imaged joints with $TUV_{joint} > upper limit of normal for the anatomically similar joint and view. These will be referred to as inflamed joints (IJ). Each joint has an anterior and posterior view: a joint is considered an IJ if either view has a <math>TUV_{joint}$ higher than the upper bound from the normative data set.

Step 3: Calculate the macrophage-involved contribution (MI) to Tc 99m tilmanocept localization for each IJ. This is done by expressing the TUV for the IJ as a fractional change from the mean TUV for the anatomically equivalent joint and view. That is, if TUV_{joint} and \overline{H}_{joint} represent the joint and view specific TUV and the mean TUV for the anatomically equivalent joint and view from the normative data set respectively, the macrophage contribution to TUV is MI_{joint}:

$$MI_{joint} = \frac{TUV_{joint} - \overline{H}_{joint}}{\overline{H}_{joint}}.$$

Step 4: TUV_{global} is the total of the macrophage-involved contributions for the IJs. (Note that MI_k is effectively 0 if TUV_{joint} is less than or equal to the upper limit of normal from the normative data set.) That is,

$$TUV_{global} = \sum_{All IJs} MI_{IJ},$$
$$TUV_{global} = \sum_{k=1}^{22} MI_k.$$

The change in TUV_{global} (Δ TUV_{global[5w]}) is the Δ % from baseline:

$$\Delta TUV_{global[5w]} = 100 \cdot \frac{TUV_{global[5w]} - TUV_{global[b]}}{TUV_{global[b]}}.$$

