The Kendall rank correlation between $\Delta TUV_{global[5w]}$ with $\Delta CDAI_{12w}$ and $\Delta CDAI_{24w}$ will be computed and a 95% confidence interval for its value will be computed using Fisher's Z-transformation. Similarly, the Kendall rank correlation between $\Delta TUV_{global[5w]}$ with changes from baseline in DAS28 and in each of the ACR Response Criteria components at weeks 12 and 24 will be computed and a 95% confidence interval for its value will be computed using Fisher's Z-transformation. The marginal distributions of the variables will be characterized with the mean, standard deviation, and the number of data pairs.

The additive effect of either quantitative or qualitative assessment of Tc 99m tilmanocept imaging will be assessed with a generalized linear mixed model with the logit link function. The patient's response status will be used as the response variable. Fixed model terms for the quantitative and qualitative plus quantitative assessments will be used. The quantitative assessment will be based on $\Delta TUV_{global[5w]}$ bucketing. Random terms will be fit for the subject and reader within subject using the variance component model. A table displaying the partial hypothesis tests (Type 3 test) for the fixed effects will be displayed.

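### Percent change in TUVglobal does not exist at baseline 0 and is unstable just above it, so the secondary change analyses need an absolute scale alongside it

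*SAP*

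**What the plan says.** SAP 2.5 counts a joint as inflamed if either of its two views is above normal. It sets that threshold as follows: "limit of normal is defined to be the upper limit of the 95% prediction interval of the joint-and-view-specific TUV in the normative data set". Each inflamed joint contributes its fractional excess over the normative mean, and TUVglobal is the sum over 22 joints. A joint whose TUV "is less than or equal to the upper limit of normal from the normative data set" contributes effectively nothing. The limits are specific to each reader.

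The same section says that the change in TUVglobal "is the Δ % from baseline", with baseline TUVglobal as the divisor. SAP 4.1.1.1 uses the same ratio, as a proportion, for Weeks 5 and 12. The protocol refers to temporal differences in TUVglobal but gives no formula, and neither document defines an absolute change.

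SAP 4.2.3 plans confidence intervals for "The Kendall rank correlation between" the 5-week change and the changes in CDAI, DAS28 and the ACR components. It adds: "The marginal distributions of the variables will be characterized with the mean, standard deviation, and the number of data pairs". SAP 2.2 runs efficacy analyses on the ITD and PP sets, "with the ITD population being the primary analysis set", and neither set requires a minimum baseline TUVglobal. The missing-data table in SAP 2.3 covers the primary endpoints only and has no row for a zero denominator.

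Protocol 3.1 has low-uptake patients imaged twice: "All subjects in this trial will undergo baseline and Week 5 scans, including those whose baseline scans demonstrate" a score under the cutoff of 5. The reason it gives is that their change is itself of interest, "as an objective is to assess if any longitudinal changes in" the score might predict clinical response or non-response.

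**The concern.** The formula fails for part of a group that the protocol deliberately rescans. A patient at baseline 0 has no percent change, so contributes no data pair to any correlation and no value to its mean or SD. A patient slightly above 0 can acquire a very large percent change when a single joint crosses its limit.

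The loss is not random. Protocol 3.1 presumes that low-uptake patients are less likely to respond, so the excluded patients sit at one end of the scale under study. Because limits and regions of interest are reader-specific, a patient may be at 0 for one reader and above 0 for another. The three by-reader parts of Table 29 could then rest on different patients.

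At stake is the interpretation of the secondary correlation objectives, chiefly Tables 29-30. Tables 31-34 are exposed too, but only for the subset imaged at Weeks 12 and 24 before Amendment 4 took effect.

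**Working it through.** **The plan's own figures.** No figure is stated for the correlation analyses or for the share of patients at or near 0. The stated sample sizes were checked with a one-sided exact binomial test at 0.025:

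| Test | n | Reject at | Power |
|---|---|---|---|
| Specificity, 0.92 against 0.80 | 98 | 87 or more | 0.908 |
| Sensitivity, 0.80 against 0.65 | 100 | 75 or more | 0.913 |
| Baseline NPV, 0.85 against 0.70 | 89 | 72 or more | 0.888 |
| Baseline NPV, 0.85 against 0.70 | 71 | 58 or more | 0.830 |

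The first two reproduce the stated 90%; the last two are close to or above the stated 90% and 80%. None uses a percent change below baseline 5, because SAP 4.1.1.1 assigns N to those patients first.

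**Is 0 reachable?** Take a patient whose joints all behave like the normative set, with a 2.5% upper tail per joint and view. With 22 × 2 = 44 independent views, P(TUVglobal = 0) = 0.975^44 = 0.33. If the two views of a joint always agree, it is 0.975^22 = 0.57. With an assumed common correlation of 0.2, 0.5 or 0.8 across all views it is 0.51, 0.70 or 0.86. This shows that 0 can occur. It does not estimate how often it occurs in RA patients.

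Suppose instead that some joints are truly raised, each exceeding its limit with an assumed probability:

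- One joint at 0.8: 0.2 × 0.975^42 = 0.07 to 0.2 × 0.975^21 = 0.12.
- Two joints at 0.8: 0.04 × 0.975^40 = 0.015 to 0.04 × 0.975^20 = 0.024.
- Two joints at 0.5: 0.25 × 0.975^40 = 0.09 to 0.25 × 0.975^20 = 0.15.

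**Patients lost.** This equals the number at baseline 0. For assumed shares of 0%, 5%, 10% and 15%, about 0, 10, 20 and 30 of 198 are lost, or 0, 30, 60 and 90 of 600.

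**Size of the low-uptake group.** SAP 1.3 tracks enrolment to secure at least 80% power for the baseline NPV. It states 71 patients below 5 for 80% power and 89 for 90%. Against the planned range this is 71/672 = 11% to 89/198 = 45%. These are requirements, not forecasts.

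**Instability near 0.** Percent change = 100 × absolute change / baseline. For an absolute change of +0.5:

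| Baseline | 0.1 | 0.5 | 1 | 5 | 20 |
|---|---|---|---|---|---|
| Percent change | +500% | +100% | +50% | +10% | +2.5% |

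The smallest non-zero score is about 1.96 × CV of the normative joint, which is 0.10 to 0.39 for an assumed CV of 5% to 20%. At that floor, one similar joint gained or lost is about +100% or -100%. The same joint is 2% to 8% of a baseline of 5.

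**Illustrative simulation.** All inputs are assumptions: N of 198 or 600, 15% to 45% of patients below 5, 0% to 15% at 0, measurement SD of 0.3 or 0.7, and a signal proportional to baseline.

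| Quantity | All with a value | Baseline 5 or more |
|---|---|---|
| SD of percent change | 23 to 51 | 20 to 21 |
| Kendall tau, percent change | 0.23 to 0.31 | 0.31 to 0.34 |
| Kendall tau, absolute change | 0.23 to 0.30 | not run |

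Patients below 5 filled 29% to 92% of the top tenth of percent changes by absolute size. The two columns describe different patients, so the difference in tau is not purely an effect of scale.

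**The case against.** The strongest reply is that little depends on this. The correlations have confidence intervals but no hypothesis test, no alpha and no sample size. Enrolment requires active RA (classification score of at least 6 and DAS28 of at least 3.2), so few patients may be at exactly 0. Kendall's tau uses ranks, which limits the leverage of extreme percentages. The number of pairs is reported, so dropped patients show as a smaller n, and Data Listing 27 gives global TUV by visit. Percent change is also the scale of the primary algorithm, so correlating it with clinical change is coherent.

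All of this stands as a limit on importance. It does not supply a value at baseline 0, and the mean and SD have no protection from ranking. A reduced n does not by itself show that the missing patients are those with the lowest uptake.

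Three stronger readings are tempting and are not supported:

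- **A third to over half of low-uptake patients are lost.** The 0.33 and 0.57 describe joints that behave like healthy controls. One or two truly raised joints can bring the probability down to a few percent.
- **Absolute change correlates better and should replace percent change.** In the simulation its tau was similar or lower. Which scale does better depends on whether the true signal is additive or proportional, and the documents do not say.
- **The ranks of low-baseline patients are mostly noise.** They can take extreme ranks through small absolute changes, but the documents contain no measurement-error data from which to say how much is noise.

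Two limits on scope also apply. No formula is given for the 24-week change, so extending the point to Tables 33-34 assumes the same ratio. The plots for Figures 1-5 are not visible, so how they would treat these patients cannot be checked.

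**Conclusion.** The point holds for the secondary change analyses. It follows from SAP 2.5 alone that a baseline of 0 is possible and that the only defined change has no value there. SAP 4.2.3 then applies that change without a minimum baseline, which undercuts the reason given in Protocol 3.1 for rescanning patients below 5. Close to 0 the percentage is unstable, and the reported means and SDs can be dominated by a few small denominators.

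A reader might infer that the trial's main result is at risk. It is not: the co-primary endpoints and the baseline-only NPV never divide by a baseline below 5.

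The number of patients affected cannot be derived from the documents; the losses shown rest on assumed shares of 0% to 15%. Neither scale is shown to give a higher tau. The gap is worth closing because the formula fails for patients the plan means to study and the remedy uses data already collected.

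**What to change.** Before database lock:

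- Keep percent change, unaltered, for the bucketing algorithms in SAP 4.1.1.1.
- In SAP 2.5, define absolute change as TUVglobal at the visit minus TUVglobal at baseline, and state that percent change is undefined at baseline 0.
- In SAP 4.2.3, Tables 29-34 and the change plots in Figures 1-5, add absolute change for every patient with both scans.
- Show percent-change correlations, means and SDs for patients with baseline TUVglobal of 5 or more.
- Report, by reader, the number of patients with baseline TUVglobal of 0.

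The cost is SAP wording, some programming and extra table rows. No new data are needed and the sample size does not change. Absolute change has its own floor effect: a baseline-0 patient can only stay or rise, and a large fall requires a high baseline. Both scales should therefore be shown, rather than one replacing the other.

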2.6 Study Center Considerations in the Data Analysis

A study center is defined as a treatment administration site or group of treatment administration sites under the control and supervision of the same Principal Investigator (PI). There will be no selective pooling of study centers.

2.7 Documentation and Other Considerations

The data analyses will be conducted using SAS[®] Software, version 9.4 or later.

3.0 Analysis of Baseline Patient Characteristics

Baseline and demographic characteristics of the safety population (i.e., those injected with tilmanocept) will be summarized for all patients in the safety population. Continuous variables will be displayed via summary statistics (mean, median, sample size, standard deviation, minimum and maximum). Categorical variables will be summarized via counts and percentages.

Detailed listings of all baseline and demographic data for each patient will also be provided as shown in Section 7 below.

4.0 Analysis of Efficacy

4.1 Description of Efficacy Variables

4.1.1 Definition of Responder/Non-Responder Status

4.1.1.1 Prediction Algorithms

The following two prediction algorithms will be defined for use in evaluating primary and secondary efficacy. Each algorithm will be used to predict a clinical response, and the subsequent prediction will be compared to the actual observed clinical response as described in Sections 4.1.2 and 4.1.3. In addition to these two prediction algorithms, the use of TUV_{global[b]} alone for the prediction of non-response will be analyzed as the key secondary efficacy variable. If TUV_{global[b]} is < 5 then the prediction is N (no improvement), otherwise, prediction is Y (improvement).

The $\Delta TUV_{global[5w]}$ values will be used to predict improvement at 12 and 24 weeks according to algorithm 1. The $\Delta TUV_{global[12w]}$ values will be used to predict improvement at 24 weeks according to algorithm 2. Both algorithms will be applied after the change in TUV calculations have been rounded to the nearest integer percentage (i.e., nearest hundredths place for a proportion).

1. ∆TUV_{global[5w]} bucketing

In the below, TUV_{global} represents the global TUV at the current time point and $TUV_{global[b]}$ represents the global TUV at baseline:

- If TUV_{global[b]} is < 5 then the prediction is N (No improvement)
- Else if

$$\Delta TUV_{global[5w]} = \frac{TUV_{global[5w]} - TUV_{global[b]}}{TUV_{global[b]}} \le -0.10$$

the prediction is Y (patient has improved). That is, a patient will be predicted as improved if TUV_{global} goes down by greater than or equal to 10%.

- Otherwise, the prediction is N.
- 2. $\Delta TUV_{global[12w]}$ bucketing

In the below, TUV_{global} represents the global TUV at the current time point and $TUV_{global[b]}$ represents the global TUV at baseline:

- If TUV_{global[b]} is < 5 then the prediction is N (No improvement)
- Else if

$$\Delta TUV_{global[12w]} = \frac{TUV_{global[12w]} - TUV_{global[b]}}{TUV_{global[b]}} \le -0.10$$

the prediction is Y (patient has improved). That is, a patient will be predicted as improved if TUV_{global} goes down by greater than or equal to 10%.

• Otherwise, the prediction is N.

Tables which display the concordance between the predictions from each algorithm vs. clinical assessment will be provided. A listing showing which algorithms provide a prediction of improvement vs. no improvement, by patient, will also be provided.

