	• To evaluate the negative predictive value (NPV) of TUV_{global} obtained before initiation of anti-TNF α therapy ($TUV_{global[b]}$) relative to a clinical non-response to therapy at 24 weeks.		
	Secondary		
	• To evaluate the sensitivity and specificity of TUV _{global} obtained before initiation of anti-TNFa therapy and at 5 weeks ± 1 week following change in therapy relative to a positive clinical response or a non-response to therapy at 12 weeks.		
	• To evaluate the NPV of TUV _{global[b]} relative to a clinical non-response to therapy at 12 weeks.		
	• To evaluate the positive predictive value (PPV), negative predictive value (NPV), and overall accuracy (OA) of TUV _{global} obtained before initiation of anti-TNFα therapy and at 5 weeks ± 1 week (ΔTUVglobal _[5w]) following change in therapy relative to a positive clinical response or a non-response to therapy at 12 and/or 24 weeks.		

Confidential Page 7 of 89

Dose(s) and Route of administration	Dose: Tilmanocept will be administered at a mass dose of 150 mcg radiolabeled with 10 mCi Tc 99m. Route of Administration: Tc 99m tilmanocept will be administered through an intravenous (IV) route of administration using a single syringe injected as a slow IV push. The preferred site of IV placement will be the left or right antecubital vein. At the completion of Tc 99m tilmanocept administration, a 10 mL sterile normal saline flush will be administered.		
Study drug	Technetium Tc 99m tilmanocept		
Duration of treatment	24 ± 1 weeks; Tc 99m tilmanocept will be administered at baseline and at Week 5. Tilmanocept will also be administered to a subset of subjects at weeks 12 and 24 (those enrolled and completing Weeks 12 and 24 prior to activation of Amendment 4).		
	 To evaluate sensitivity and specificity in patient subgroups. To evaluate the safety of IV-administered tilmanocept radiolabeled with Tc 99m. 		
	To evaluate the correlation of changes with TUV _{global} and changes in clinical RA assessments as a means to monitor therapy. The state of the correlation of changes with TUV _{global} and changes in clinical RA assessments as a means to monitor therapy.		
	• To evaluate the correlation of changes in TUV _{global} obtained before initiation of anti-TNFα therapy and at 5 weeks ± 1 week following a change in therapy with changes in clinical assessments at 12 and/or 24 weeks for specific anti-TNFα bDMARD agents.		

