7 STUDY PROCEDURES

7.1 Schedule of Evaluations

A schedule of evaluations is provided in the Schedule of Study Events (see Appendix 1). Visits 7 and 9 have been eliminated per Protocol Amendment 4. For continuity, visits have not been renumbered (i.e., Visit 6 is followed by Visit 8).

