QTcF	QT interval with Fridericia's correction formula		
RA	rheumatoid arthritis		
ROI	region of interest		
SAE	serious adverse event		

List of Abbreviations and Definitions of Terms

Term	Definition
SAP	statistical analysis plan
SJC	swollen joint count
SOC	system organ class
SPECT	single photon emission computed tomography
Tc 99m	technetium-99m metastable isotope; γ -emitting (half-life 6.02
	h)
TEAE	treatment-emergent adverse event
TESAE	treatment-emergent serious adverse event
tilmanocept	DTPA Mannosyl Dextran (the US Adopted Name for the drug
	substance of Lymphoseek)
TJC	tender joint count
TUV	Tilmanocept uptake value
US	United States
WPI	Widespread Pain Index

INTRODUCTION

Description

This statistical analysis plan (SAP) is consistent with Amendment #3 of the study protocol (dated 29 September 2023) and includes details of efficacy and safety summaries for use in support of the planned trial, as outlined in ICH E3 (Structure and Content of Clinical Study Reports) and ICH E9 (Statistical Principles for Clinical Trials). Considerations were also given to the FDA Guidance for industry on Developing Medical Imaging Drug and Biological Products Part 3: Design, Analysis, and Interpretation of Clinical Studies (June 2004), FDA Guidance for Industry on Clinical Trial Imaging Endpoint Process Standards (April 2018) and Statistical Guidance on Reporting Results from Studies Evaluating Diagnostic Tests - Guidance for Industry and FDA Staff (March 2007). The study design and analysis plans align with recommendations received from the US FDA at the End of Phase 2 meeting on 01 September 2021 (IND 132943).

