1.3 Sample Size

NAV3-33 is sized with respect to achieving specified goals in the co-primary endpoints of sensitivity and specificity of $\Delta TUV_{global[5w]}$ with bucketing. Sensitivity and specificity require knowledge of the patient's clinical status at Week 24, and so hypothesis testing will be performed after classification. The value of $\Delta TUV_{global[5w]}$ necessary to predict response vs. non-response and the value of $TUV_{global[5w]}$ necessary to predict response vs. non-response and the value of TUV_{global[b]} at baseline necessary to predict non-response will be determined in advance. The classification procedure occurs in two stages, following the baseline image acquisition and (possibly) following the 5 week image acquisition and calculation of $\Delta TUV_{global[5w]}$. After the baseline imaging, patients whose TUV_{global[5w]} is available, patients whose TUV_{global[b]} is ≥ 5 and D% is $\leq -10\%$ are predicted to be responders. All other patients are predicted to be non-responders. The Week 24 ACR50 will be used as the primary determination of clinical response for the reference standard

The hypotheses for the co-primary endpoints to be tested are:

$$H_{O1}: \pi_{Sp} \le 0.8$$

 $H_{A1}: \pi_{Sp} > 0.8;$

And

 $H_{02}: \pi_{Se} \le 0.65$ $H_{A2}: \pi_{Se} > 0.65.$

In the above π_{Sp} represents the true specificity of the classification procedure and π_{Se} represents the true sensitivity of the classification procedure when used to predict the outcome of the anti-TNF α bDMARD inhibitor therapy at 24 weeks. An overall two-tailed Type I error rate of 0.05 (one-tailed 0.025) was used without adjusting for multiple endpoints, as both co-primary endpoints must be achieved in order to have a successful study. If the actual specificity is 0.92 and the actual sensitivity is 0.8, and if an exact binomial test is used to test the above hypotheses, a total of 98 clinical non-responders and 100 clinical responders are needed for 90% power of the individual tests. That is, a minimum of 198 total patients is needed. This applies to a single reader.

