To evaluate the power characteristics of this process with 3 correlated readers where at least the same two of the three readers must reject both null hypotheses above, a simulation study was performed. Correlated binomial random variables were generated using a copula. The hypotheses were tested for each simulated reader using an exact binomial test, and the number of iterations where at least the same two of the three readers rejected both hypotheses was counted. Under the conditions above this procedure has power 0.93 when $\rho = 0.7$ and 0.89 when $\rho = 0.9$.

In Arm 3 of the NAV3-31 study a ratio of 5 non-responders to 1 responder was observed. If this ratio is maintained in NAV3-33 for the $\Delta TUV_{global[5w]}$ with bucketing predictions, a total of 600 patients is needed to achieve the desired power. That is, a total of 500 clinical non-responder patients is expected to be enrolled before reaching the required 100 clinical responders.

Taking into account a 10% dropout rate, the anticipated total sample size for the study is approximately 672 patients (560 clinical non-responders and 112 clinical responders). That is:

- Clinical Non-Responders: 90% completion rate relative to 560 enrolled patients will result in 500 completed patients
- Clinical Responders: 90% completion rate relative to 112 enrolled patients will result in 100 completed patients

Because there is uncertainty about how responding and non-responding patients will enroll, enrollment may continue until at least 560 clinical non-responders and 112 clinical responders are participating in the study. The cumulative enrollment of clinical non-responders and responders will be tracked throughout the study in order to stop enrollment once the required number has been reached for each clinical category. This tracking of clinical response and non-response status will be performed by individuals without knowledge of the TUV data. At the Sponsor's discretion, the week 12 clinical response outcomes may be used to help track enrollment.

If the two co-primary endpoints are achieved (i.e., both null hypotheses are rejected for at least the same 2 out of 3 readers), then the following hypotheses will be tested at one-tailed 0.025 for the key secondary endpoint of NPV of TUV_{global[b]} with respect to ACR50 at week 24:

$$H_{03}: \pi_{\text{NPV}} \le 0.7$$

 $H_{A3}: \pi_{\text{NPV}} > 0.7;$

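### The Week 12 bucketing tables have no analysis set matched to Amendment 4: read directly, they keep every low-baseline patient but only the scanned high-baseline patients, so sensitivity reads too low and specificity modestly too high

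*SAP*

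**What the plan says.** **Who has a Week 12 scan.** The Protocol Synopsis (Duration of treatment) states that "Tilmanocept will also be administered to a subset of subjects at weeks 12 and 24", and limits that subset to subjects enrolled and through both visits before Amendment 4 was activated. Protocol 8.4.1 now schedules imaging at Visits 2 and 4 only, and Protocol 7.1 adds that "Visits 7 and 9 have been eliminated per Protocol Amendment 4".

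**What the SAP assumes.** Its Introduction says that it "is consistent with Amendment #3 of the study protocol". SAP 1.2 still describes imaging at Weeks 5, 12 and 24 for patients in general. The Week 12 algorithm remains an objective (1.0), an endpoint (4.1.4) and Tables 15-16 (7.0). SAP 4.2.3 promises exact intervals and per-reader p-values for sensitivity and specificity, although the Table 15 shell shows no p-value. The current protocol has dropped the Week 12-scan prediction objective (2.3) but keeps the endpoint (9.3.3).

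**The rule.** The 12-week change "values will be used to predict improvement at 24 weeks according to algorithm 2". Algorithm 2 tests the baseline first: below 5 is a predicted non-response. Only patients at 5 or above go on to the test of a fall of at least 10% at Week 12.

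**Missing scans.** SAP 2.2 lets a patient be left out of an ITD analysis when missing imaging or clinical data prevent a prediction. The matching sentence in Protocol 9.5.1 names only Day 0 imaging. The table in SAP 2.3 covers the primary endpoints, and its only rule for a follow-up scan concerns Week 5. Neither document says what happens when the Week 12 scan is absent.

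**The concern.** The two baseline buckets do not need the same data. Below 5, a prediction exists whether or not the patient was scanned at Week 12. At 5 or above, it exists only with the scan. If patients without a possible prediction are dropped, the table combines a complete group of automatic negatives with a fraction of the patients who could test positive.

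Responders with low baseline uptake, all of them missed by the rule, are then over-represented in the sensitivity denominator. Non-responders with low baseline uptake, all correctly classified, are over-represented in the specificity denominator. A reader would take the result as the performance of a Week 12 scan, when part of it reflects who was scanned before the amendment.

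**Working it through.** **Planning values.** The documents give no accuracy figure for the Week 12 algorithm, so I carry over the Week 5 planning values as an assumption: "If the actual specificity is 0.92 and the actual sensitivity is 0.8". SAP 1.3 states that "a total of 98 clinical non-responders and 100 clinical responders are needed for 90% power of the individual tests", and this reproduces with a one-sided exact binomial test at 0.025:

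- n = 98, reject at 87 or more: alpha 0.0158, power 0.908.
- n = 100, reject at 75 or more: alpha 0.0211, power 0.913.

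**Other inputs.**

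- Mix: "In Arm 3 of the NAV3-31 study a ratio of 5 non-responders to 1 responder was observed", which SAP 1.3 turns into 500 and 100 completers.
- Shares below 5 are not given. I match them to the key secondary plan of 89 predicted non-responders at NPV 0.85, taken as 89 of the 600 completers (my assumption). Responders below 5: 0.15 × 89 = 13.35, so qR = 13.35/100 = 0.1335. Non-responders below 5: 0.85 × 89 = 75.65, so qN = 75.65/500 = 0.1513.
- Scanned share f is not given, so it is varied. Scanning is taken as unrelated to baseline uptake and outcome.

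**Formulas.** Of all responders, qR + f(1 − qR) enter the table and f·Se are true positives. Of all non-responders, qN + f(1 − qN) enter and f(1 − Sp) are false positives. So

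- Se shown = f·Se / [qR + f(1 − qR)]
- Sp shown = 1 − f(1 − Sp) / [qN + f(1 − qN)]

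At f = 0.25: Se = 0.20 / (0.1335 + 0.2166) = 0.20/0.3501 = 0.571, and Sp = 1 − 0.02 / (0.1513 + 0.2122) = 1 − 0.02/0.3635 = 0.945.

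| f | Se shown | Sp shown | Share of table below 5 |
|---|---|---|---|
| 0.10 | 0.36 | 0.966 | 64% |
| 0.25 | 0.57 | 0.945 | 41% |
| 0.50 | 0.71 | 0.931 | 26% |
| 0.75 | 0.77 | 0.924 | 19% |
| 1.00 | 0.80 | 0.920 | 15% |

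Sensitivity shown equals the co-primary null of 0.65 when 0.80f = 0.65(0.1335 + 0.8665f), that is f = 0.0868/0.2368, about 0.37. Below that scanned share, a rule with true sensitivity 0.80 would read under 0.65.

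**Range.** Four other assumed pairs, with qR from 0.05 to 0.15 and qN from 0.15 to 0.50, give Se 0.55-0.70 and Sp 0.945-0.968 at f = 0.25, and Se 0.70-0.76 and Sp 0.930-0.947 at f = 0.50. All four imply a baseline NPV above the planned 0.85, so the matched pair stays closest to the plan.

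**After restriction to patients with both scans.** Numerators and denominators are all scaled by f, so 0.80 and 0.92 are recovered at any f. What remains is imprecision: f = 0.25 leaves about 25 responders and 125 non-responders (95% Clopper-Pearson interval for Se 0.59-0.93). At f = 0.50 there are about 50 and 250 (0.66-0.90).

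**The case against.** **This is version lag, and a programmer would use scanned patients anyway.** Under Amendment 3 everyone was to be scanned, so nobody was selected by design. SAP 4.1.1.1 also says that the algorithms are applied once the changes have been calculated and rounded, which could mean that a calculated Week 12 change is required of every patient. Both points are fair. They show that the cause is an unaligned document rather than a deliberate choice, and that the text is ambiguous. They do not settle it: the first branch needs no change value, and no passage restricts Tables 15-16 to scanned patients.

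**Stronger readings a reader might infer, and why they fail.**

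- *Unscanned patients at 5 or above fall into the final negative branch.* At f = 0.25 this gives Se 0.20 and Sp 0.98. Algorithm 1 has the same closing branch, yet SAP 2.3 treats a missing Week 5 scan at baseline 5 or above as missing and imputes it. That branch is therefore not meant to absorb absent scans.
- *The Week 5 mean imputation carries over.* At f = 0.25 this gives Se 0.35 and Sp 0.83. SAP 2.3 is confined to the primary endpoints and does not name Week 12.
- *Specificity is inflated to 0.96-0.97.* At a scanned share of about 0.30, that takes 40-60% of non-responders and 5-15% of responders below 5. At the 5:1 mix the implied baseline NPV is 2/2.15 = 0.93 to 3/3.05 = 0.98, against the planned 0.85.
- *Tables 31-34 and Figures 1-5 share the bias.* They use observed changes, so a scan is needed by construction and there is no automatic negative. The correlation tables already print n.

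**Conclusion.** The concern holds on the most direct reading of SAP 4.1.1.1 together with 2.2. Sensitivity in Tables 15-16 is biased down whenever fewer than all patients have a Week 12 scan and some responders have baseline TUVglobal below 5. Specificity is biased up under the same condition on non-responders, but modestly.

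With shares below 5 matched to the planned NPV, true values of 0.80 and 0.92 would be shown as about 0.57 and 0.945 at a scanned share of 0.25, and 0.71 and 0.931 at 0.50. The direction follows from the rule. The size rests on assumed values for the scanned share, the shares below 5 and the Week 12 accuracy.

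The consequence is confined to one secondary endpoint outside the gated hypotheses. A reader might infer that the main results are affected as well. They are not, because the co-primary and key secondary endpoints use baseline and Week 5 scans, which remain planned for all subjects.

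**What to change.** Align the SAP with Amendment 4. In SAP 4.1.1.1, 4.2.3 and Tables 15-16, restrict algorithm 2 to patients with both a baseline and a Week 12 scan, whichever side of 5 their baseline falls. State the n and label the result a descriptive pre-Amendment-4 subset analysis.

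Add a note that the Synopsis defines the subset by completion of Weeks 12 and 24. It may therefore under-represent patients who stopped early, including those whom SAP 2.3 would count as non-responders. The restriction removes the selection on baseline uptake, but not this one.

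Tables 31-34 and the Week 12 and 24 points of Figures 1-5 need at most a subset label.

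The cost is SAP wording, a population flag, and a visibly smaller and less precise secondary endpoint.
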